SORF rating from the home observation of the parent engaged in interaction with the child in everyday activities (meals and snacks, caregiving, play with toys or objects, play with people, book sharing, and family chores. The ESAC and SORF were chosen because these are the only empirically-supported screening tools for ASD at this age. FSU has extensive experience conducting screening and diagnostic evaluations of infants and toddlers using these tools and will oversee selection of referrals for this study. For high-risk infants, the selection criterion for participation in this treatment study is a positive screen on 2 of the 4 autism-specific screening tools with one of those positive screens being a SORF. For low-risk infants, selection criteria for participation includes a positive screen on both SORF measures and one additional measure (e.g., 3 out of 4 measures). The purpose of this early treatment study is to contribute to the overarching aims of the Emory ACE Center to study risk and resilience in ASD. Therefore, we are targeting infants who are genetically at risk and who show early signs of autism and communication delay. Thus, we are casting a broader net than only children who will end up with a diagnosis of ASD but are selecting siblings who are at the highest risk for having ASD or a developmental delay.

Random Assignment of Participants to Experimental Groups. Children who meet the selection criteria and whose parents give consent to participate in the study will be given a computer-generated random assignment to one of two groups- Group plus Individual or Group alone. As a complement to random assignment, we will covary pretest variables that end up being correlated with the outcome variables, in our statistical analysis, if the groups are not equivalent on these variables. The diagnosticians for all measures and raters for intervention fidelity and treatment mediators will be kept blind to group assignment.

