Sample Retention and Attrition. Our strategies to promote retention are particularly geared for families with environmental risks and include: 1) assisting families in filling out questionnaires and maintaining frequent contact to remind them about returning forms and upcoming appointments; 2) coordination of appointments with other agencies; 3) offering small financial incentives to compensate for their time for assessment visits; 4) offering families an hour a month of consultation to provide information needed about ASD and to coordinate referrals to other agencies; and 5) to provide the 2 weekly Individual sessions in the home and incorporate the families' everyday activities. Because the Group only group is at a greater risk for attrition, we have made an effort to design that treatment to be appealing to families by offering it weekly and have limited the length to 9 months. In Georgia, the public Part C early intervention programs for children under 36 months do not offer specialized or intensive services for children with autism or ASD. Like the majority of states, non-categorical eligibility based on developmental delay is customary and the usual services provided in these states are 1 to 3 hours of clinician-implemented therapy per week. Thus, it is anticipated that both groups will utilize the community services comparably and that because of the low intensity of community services, they are not anticipated to diffuse Individual treatment effects, and may actually contribute to retention in this study. That is, families will be motivated to participate in Group or Individual as a supplement to community services. Because the parents of children in this study have an older sibling with ASD, they will be more motivated to participate in early intervention for the high-risk sibling showing early diagnostic features of ASD. We anticipate a possible attrition rate between 10 and 12%. With this attrition rate, we will complete intervention for at least 80 children.

Timeline for Assessment Measures and Intervention Activities.

Infants will be recruited during Years 2 and 3 of the Emory ACE, 46 children in each year totaling 92 children. Children will be followed until 36 months of age and follow up assessments will be

completed during years 3-5. The timeline for assessment measures and intervention activities is included in Appendix 1.

Dependent Variables [CAC= Emory ACE Clinical Assessment Core (IRB#65732)]

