The home observation measure will be collected monthly as the context to chart developmental trajectories of mediator variables. This context provides an hour of parent-child interaction during a variety of everyday activities in the natural environment without the clinician present and is an index of generalization of parent and child learning over the course of the treatment study. It is hypothesized that parent implementation of transactional supports is a mediator of child active engagement, which is a mediator of treatment outcome. These mediators will be evaluated from the monthly home observations with the Measure of Active Engagement and Transactional Supports (MAETS; see Appendix 2) at baseline through 36 months of age. Specifically, these home observations will be completed monthly during the 9 month intervention period and then quarterly through the child's 36 month birthday. It is also hypothesized that the measures available through Projects I and II, of social visual and vocal engagement, are mediating variables, and will be examined in relation to the MAETS and outcomes on dependent variables for children in the two treatment conditions.

Moderator Variables

Demographic Information. Parents will be asked to provide demographic information about

race, ethnicity, and socioeconomic level as possible moderators of treatment effect. (see CAC) **Baby Siblings Research Consortium Intervention History Form**. The number of hours of other intervention outside of ESI will be documented and updated by a parent monthly. This form documents the hours in psychosocial or educational treatments and whether the child is receiving alternative treatments (e.g., diet, chelation). The total number of hours per week of combined therapies and intervention multiplied by the number of weeks received will be calculated. (see Appendix 2)

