Data Analytic Strategy. The main research aims and hypotheses will be analyzed using a series of mixed models, focusing on Growth Curve Modeling (GCM) and Random-Effects Regression (RER) as more powerful alternatives to repeated measures ANOVA, and estimates of effect sizes will be obtained. We anticipate that effect size estimates will be conservatively derived from simple inspection of observed differences in treatment versus control means divided by the appropriate standardizer (either the control standard deviation or the pooled standard deviation, depending upon whether the treatment is inducing group differences in variances or not). The research aims compare growth trajectories (or residualized change, or outcome only, depending on the dependent variable of interest) for children in the treatment and control groups. It is hypothesized that children receiving the Group plus Individual condition will show significantly faster growth trajectories or change on the MAETS, which will mediate social communication, autism symptoms, developmental level, and adaptive behavior outcomes. Unconditional models that vary in complexity will be used to determine the most parsimonious models for estimating growth in this sample. After fitting the overall model, we will perform fixed-effects contrasts to test for cross-sectional differences between the two groups at points along the curve. Aims 2 and 3 build upon these models to investigate potential mediator and moderator variables that may predict response to treatment. Moderator variables such as initial level of child or parent performance and measures of family functioning will be interacted with treatment group to investigate potential moderating relationships. To investigate potential mediators of treatment effectiveness such as MAETS, we will follow standard strategy for testing mediational effects in a multilevel design where fidelity is conceptualized as a level 1 mediator that can vary by time. Finally, we will consider the possibility that the mediated relation may be stronger in one subgroup than the other (moderated mediation), either because treatment fidelity is accomplished to a greater extent in one subgroup than another or because the link between treatment fidelity and outcome is stronger in one subgroup than another (e.g., treatment fidelity predicts outcome only in individuals with sufficient cognitive abilities). In addition to existing GCM/RER analyses, in synergy with Projects I & II we will repeat our analyses using Functional Data Analysis, a new approach that significantly improves both the detection of common features in trajectory shape as well as the identification of individual spurts or delays relative to the group. Project III will rely on the Data Management and Analysis Core for data storage, management, and transmission to NDAR.

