
Attrition Analyses. All analysis will be done using an intention to treat approach. That is, every subject in the study will be considered in the analysis as a member of the treatment group to which s/he was assigned. We will conduct a series of analyses to examine attrition and its potential effect on the results ⁶⁹, including examining the differential attrition rates for the two treatments and for child and parent characteristics of those completing and those who did not complete one or both treatment conditions, different definitions of dropout, different outcome measures, and treatment-correlated attrition. For the HLM analyses with multiple time points, missing data are not a concern, but differential attrition by treatment group would be. If differential attrition appeared to be a problem, then we would conduct multiple imputation of missing data ⁹⁵ to attempt to estimate the appropriate effect sizes and confidence intervals.

Power Analyses. Power for growth curve modeling was estimated using a power estimation program developed for HLM models 61. When estimating power in growth curve models, there are a number of factors that need to be considered. In addition to alpha level, number of subjects, and anticipated effect size, power can also vary as a function of the number of observations employed and the duration of the study. For these power analyses, we set alpha at .05 and we anticipated as few as 5 and as many as 25 observations per child (per measure). Additionally, we estimated that there would be approximately 10 times as much within person variability than between person variability (the ICC for the person level effect would be .10). Using these estimates, we anticipate that 92 subjects would give us a power=.90 to detect an effect of d=.50 (which corresponds to a medium effect) with five time points estimating linear change. For models testing treatment differences in the presence of quadratic change (with 15 or more assessments per child), power is .95. If attrition drops the sample size to 80 subjects, we will still have power equal to .86 to detect a medium-sized effect (with five assessments estimating linear change) and power=. 91 for those treatment differences tested in the presence of quadratic change. Thus, the minimum power to detect medium effects with 80 subjects is .86. We anticipate that the use of FDA and PACE will increase power.

7. Risks

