All information that is collected in connection with this study will remain confidential and will only be disclosed as required by U.S. or State law. Examples of information that we are legally required to disclose include abuse of a child or elderly person, or certain reportable diseases. Every foreseeable precaution to protect confidentiality will be taken. As in all research studies, the potential risk for a loss of confidentiality exists (i.e., computer viruses, computer hackers). However, every reasonable precautionary measure will be taken to protect confidentiality of all data. Computers will regularly be updated for virus protection.

9. Data and Safety Monitoring Plan

Although minimal risks are anticipated, a Data and Safety Monitoring Plan (DSMP) will be established and will be responsible for data and safety monitoring. The DSMP will include the PI, Project Coordinator, and the Family Resource Coordinator from each site and will be headed by the PI. The DSMP will include a monthly meeting. across-site DSMP members will meet every six months through teleconference for review of child and family progress and inspection of the reliability of assessment measures and treatment fidelity measures to ensure the validity and integrity of the data. If any adverse events are identified, an adverse event report will be provided to the IRB at Emory and FSU and the funding Institute and Center. If children show an extremely slow rate of progress or regression, parents will be encouraged to increase

community resources that are available in the same way as they would be in our clinic. Other treatments will be considered as covariates of treatment effects. Although this may make interpreting the data more difficult, it would be unethical to deny children more intense treatment because of our research.

This research project proposes to manage data using Emory Amazon Web Services (Emory AWS), which is an Emory customized implementation of the Amazon Web Services ondemand cloud infrastructure for high-performance computing, data storage, database management, data sharing and hosting. Emory AWS provides investigators with access to many of the key research computing services offered by AWS. Additional security and technical controls help ensure that data are protected from unauthorized use, and that data storage and processing are conducted in a standardized, secure and HIPAA-eligible environment.

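### If outside treatments received after randomisation enter the Aim 1 models as covariates, which section 9 leaves open, the arm estimate is no longer the effect of assignment, though the likely shift is small

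*Combined protocol and SAP*

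**What the plan says.** All references are to the combined protocol and SAP.

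- **Section 9, Data and Safety Monitoring Plan.** "If children show an extremely slow rate of progress or regression, parents will be encouraged to increase" the community resources open to them. The next sentence reads: "Other treatments will be considered as covariates of treatment effects". The section then concedes that interpretation may become harder, and explains that withholding more treatment would be unethical. It names no aim, model, time window or form for the covariate.
- **Section 5, Moderator Variables.** "The number of hours of other intervention outside of ESI will be documented and updated by a parent monthly". A total is then formed as weekly hours times weeks received.
- **Section 5, Random Assignment.** For covariates, "we will covary pretest variables that end up being correlated with the outcome variables", if the arms are not equivalent on them.
- **Section 5, Sample Retention and Attrition.** On uptake, "it is anticipated that both groups will utilize the community services comparably". On whether outside services could dilute the comparison, the plan gives this reason for expecting none: "because of the low intensity of community services, they are not anticipated to diffuse Individual treatment effects".
- **Section 6, Data Analytic Strategy.** Outside treatment is not mentioned. On moderators: "Moderator variables such as initial level of child or parent performance and measures of family functioning will be interacted with treatment group".
- **Section 6, Attrition Analyses.** Intention to treat applies to all analyses and is defined so that "every subject in the study will be considered in the analysis as a member of the treatment group to which s/he was assigned".

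**The concern.** A pretest covariate cannot be affected by assignment, so adjusting for it leaves the target of estimation alone. Outside hours are different. They accrue during follow-up, and section 9 raises them for children who are doing badly. If Individual works, fewer children in that arm should be flagged, and that arm should accrue fewer hours. Within each arm, more hours would then mark a poorer prognosis. A model that holds hours fixed compares children who reached the same hours by different routes, and part of the treatment difference is absorbed into the hours coefficient.

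Keeping every child in the assigned arm does not prevent this, because the intention-to-treat definition in section 6 governs arm membership and is silent on covariates. What is at stake is the meaning of the Aim 1 estimate. A reader could not correct it afterwards, because the direction of the shift is not fixed.

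**Working it through.** **1. Is the covariate role settled?** Section 9 points to adjustment. The heading in section 5 points to moderation. The Random Assignment paragraph names pretest covariates without excluding others. Section 6 is silent. Together these neither commit Aim 1 to adjusting for later hours nor forbid it.

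**2. Plan figures.** There is no figure for uptake or for the share of slow progressors, so none can be reproduced. From the power paragraph in section 6 only d = .50 is used, as the true effect. The stated power (.90 with 92 children) plays no part here.

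**3. Single-outcome model (all inputs other than d assumed).** Early progress is e·A + e1, where A = 1 for Group plus Individual, e is the early effect and e1 is standard normal. A child is flagged below the cut that flags a share c of the Group arm. A share u of flagged children add k weekly hours to a background with SD s. The outcome is Y = .5A + rho·e1 + sqrt(1 − rho²)·e2. Then

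adjusted d = .50 − beta × (mean hours, Individual arm minus Group arm), with beta = pooled within-arm cov(Y, hours) / var(hours).

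Worked case: c = .10, k = 5, rho = .6, s = 2, e = .25, u = 1.

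- Flagged: Group .10; Individual Φ(−1.2816 − .25) = .0628.
- Hours difference: 5 × (.0628 − .10) = −.186.
- Covariance: Group −.6 × 5 × .1755 = −.526; Individual −.6 × 5 × .1235 = −.370; mean −.448.
- Variance: Group 4 + 25 × .10 × .90 = 6.25; Individual 4 + 25 × .0628 × .9372 = 5.47; mean 5.86.
- beta = −.448 / 5.86 = −.0765.
- Adjusted d = .50 − (−.0765)(−.186) = .50 − .014 = **.486**.

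**4. Range.** The grid is c = .05, .10, .20, .30; k = 2, 5; rho = .5, .6, .7; s = .58, 2, 3; e = .10, .25, .50; u = .5, 1. That is 4 × 2 × 3 × 3 × 3 × 2 = 432 cases. The smallest s is a uniform spread over the 1 to 3 weekly hours that section 5 calls usual: 2/√12 = .58.

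| Cases | Minimum | Median |
|---|---|---|
| All 432 | .336 | .494 |
| c of .10 or less | .426 | .497 |
| k = 2 | .382 | .497 |

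The maximum is .500, and 399 of 432 cases (92%) stay at .45 or above. The minimum needs c = .30, k = 5, rho = .7, s = .58, e = .50 and u = 1 together.

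**5. Direction.** Step 3 gives outside hours no benefit. If one weekly hour is worth g SD, the effect of assignment becomes .50 + g × (hours difference), while the adjusted figure does not change. The adjusted estimate is then too high once g exceeds −beta, which is .077 in the worked case and .04 to .20 over other inputs tried. It also reverses if better-resourced families obtain both more hours and better outcomes; section 3 describes unequal access. At c = .10, s = 2, e = .50 and u = 1, with 2 hours and .3 SD of outcome per SD of resources, it is .507. With no treatment effect and equal uptake the shift is zero.

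**6. Growth model.** This was simulated at the five social communication ages in section 5 (12, 15, 21, 24 and 36 months), with 5 extra hours, a flag at 18 months, full take-up and the arm-by-time difference scaled to .50.

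| Flagged, background | Hours-by-time term | Time-varying weekly hours |
|---|---|---|
| 20%, 1–3 hours | .414 | .457 |
| 20%, SD 2 | .470 | .474 |
| 10%, 1–3 hours | .453 | .474 |
| 10%, SD 2 | .488 | .488 |

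When total hours entered as a main effect only (20%, 1–3 hours), the arm-by-time term stayed at .500, but the 36-month contrast became .483.

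**7. Second check.** A separate large-sample simulation, also on assumed inputs, gave .49, .46 and .41 as the link from slow progress to uptake strengthened, with no direct effect of arm on uptake. Allowing a direct arm difference of .3 SD in uptake, either way, gave shifts from −.18 to +.09.

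**The case against.** The strongest reply is that the plan probably means something else. The outside-hours form is listed among moderators, which suits Aim 3. The moderator list in section 6 is illustrative, so it does not shut hours out. The only covariate rule written for the outcome comparison concerns pretest variables. The section 9 sentence sits in an ethics explanation and promises only consideration. This stands as a plausible reading, and it is why the point is conditional.

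Next, Aim 1 concerns trajectories, and a per-child total entered as an ordinary covariate leaves the arm-by-time term unchanged. That is correct, but it does not dispose of the matter. Section 6 also provides for residualised change, outcome-only models and contrasts at points along the curve, and there a main-effect covariate does move the estimate.

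Finally, 5 extra weekly hours is a lot where 1 to 3 is usual and the local public programme has no intensive autism service. That also stands. With 2 extra hours and a background SD of 2 or 3, every case is at .474 or above. With 2 hours and SD .58 the minimum is .38, so the shift is not always trivial. The expectation of comparable use also favours a negligible shift, but it is an expectation, and the slow-progress rule works against it if Individual is effective.

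**Conclusion.** The point holds in conditional form, at low severity. If outside hours received after randomisation are covariates in Aim 1, the arm estimate is not the effect of assignment. Under assumed inputs the shift is usually about .01 in d (median .49 against .50) and reaches .16 at the extreme (.34). If Individual works and outside services are weak, as section 5 expects, it runs towards no difference; otherwise it can run the other way. It is nil if uptake depends on neither arm nor progress.

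A reader might infer more, and the documents do not support it:

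- *That the plan commits Aim 1 to this adjustment.* No section says so.
- *That the Aim 1 result will be materially biased.* There are no uptake data, and most assumed cases move little.
- *That the stated power is lost.* The form in which hours would enter is not given.
- *That the open choice inflates false positives.* That requires reporting whichever analysis is significant, and nothing in the documents suggests it.

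**What to change.** - In section 9, replace the covariate sentence with: *Treatments received after randomisation will not be covariates in the main Aim 1 models.*
- In section 6, limit Aim 1 covariates to pretest variables, in line with the Random Assignment paragraph of section 5. Outside hours received before randomisation may be among them.
- Report later outside hours by arm beside the intention-to-treat result. This also tests the expectation of comparable use.
- Label any analysis that accounts for later hours as secondary or sensitivity, and state its estimand and how hours enter. No particular method is required with 80 to 92 children.
- Leave the encouragement to families as it is.

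The cost is wording changes in two sections and one table from data already collected. No visits, measures or participants are added.
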